This is a randomized trial with a 2x2 factorial design to examine the comparative effectiveness of two PDAs and an in-visit intervention. In the study, patients will be surveyed shortly before their initial visit with an orthopedic specialist and again about 1 week and 1 year after the visit. Patients scheduled for an appointment with the orthopedic specialist will be screened for eligibility (criteria are listed in Table 1) and if eligible, will be randomized to receive either the Health Dialog or Healthwise decision aids to review before their visit. A computer generated randomization allocation sequence will be created for participants. Eligible patients will receive a cover letter and an information sheet about the study that includes instructions about how to opt-out in the mail before their visit. Those who do not opt out will then be enrolled in the study. The random assignment originally assigned to patients who are found ineligible after their visit will be put back to the queue and become available for the next eligible patient.

Providers will be randomly assigned to usual care or intervention group (a worksheet which includes patient’s goals and preferences). Providers in the worksheet group will receive short training on the use of the worksheet.

The study will enroll patients at three sites: an academic center, the Arthroplasty Department at Massachusetts General Hospital (MGH), a community hospital, Kaplan Joint Center at Newton Wellesley Hospital (NWH), and an orthopedic specialty hospital, New England Baptist Hospital (NEBH). MGH and NWH share common resources that are critical to the conduct of the study, including patient registries which routinely collect similar patient reported data and clinical outcomes for hip and knee osteoarthritis patients. Both these sites also have access to both

[figure not shown]
Healthwise and Health Dialog decision aids through Partners Healthcare’s contracts with those vendors. NEBH is not a Partners-affiliated hospital and therefore requires separate coordination efforts to execute the research study.

Table 1: Eligibility for survey study

	Eligible	Ineligible

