New patients coming to see a specialist in the Arthroplasty group at MGH complete surveys in the clinic via a computer or tablet. The surveys cover quality of life, pain, functioning and symptoms and are administered through the Harris Joint Registry (IRB # 2002-P-001823). The surveys for this study will be incorporated as an additional module in the Harris joint registry for arthroplasty patients at MGH and will be administered by paper, by computer in the clinic or via Redcap depending on the patients' preference and the timing of the visit. The new patients at NWH will similarly be offered to complete the patient reported quality and functional status surveys by paper, by computer or tablet in the clinic, or by email in advance of their visit as covered by their patient reported outcome registry protocol (IRB protocol 2014P000696). New patients at NEBH will be asked to complete the quality of life surveys as part of the initial pre-visit survey for the study.

Briefly describe study procedures. Include any local site restrictions, for example, "Subjects enrolled at Partners will not participate in the pharmacokinetic portion of the study." Describe study endpoints.

Study Procedures:

1. The principal investigator will obtain permission from participating clinicians at each site to screen their patients for eligibility and enroll eligible patients onto the study. Some, but not all, participating clinicians may also be co-investigators.
2. The statistician will generate a random allocation sequence to indicate which decision aid each participant should receive. The statistician will also group providers at each site by patient

volume and randomly assign each group to the usual care or intervention group for the in visit intervention.

3. The research coordinator, with support from the research nurse or other clinic staff, will review the schedules of participating clinicians and the Epic research report, if available, to complete the eligibility screener to the extent possible and identify potentially eligible participants

4. The research coordinator may call potentially eligible patients to clarify any information about eligibility.

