Provider randomization will be stratified by site. Within each site, surgeons will be divided into two groups with similar patient volume. One of the two groups will be randomly assigned to usual care and the other to receive the in-visit worksheet. It will not be possible to blind the research staff, patient or providers to the group assignment for providers; however, those entering data and those analyzing the data will be blinded to group assignment.

A computer-generated randomization allocation sequence will be created for patients from each site. After confirming eligibility, the staff at the Health Decision Sciences Center that fulfills PDA orders will have access to the sequence in order to deliver the appropriate decision aid. The staff who fulfill the orders will not be the same staff that approach patients in clinic. To the extent possible, the research staff calling participants on the phone and/or approaching them in clinic will be blinded to the PDA assignment. In our pilot, several patients brought the decision aid to the clinic with them, and as a result, it was clear which intervention they received. Patient participants have the opportunity to opt-out before their visit, and those who do not opt out will be enrolled in the study. The random assignment originally assigned to subjects who are found ineligible will be put back to the queue and become available for the next eligible subject.

Patient participants will not be blinded to the PDA assigned to them; however, they will not be given any explicit information on the surgeon assignment. Likewise, surgeons will not be blinded

to their intervention group, but they will not be given any information on the type of PDA the patient used. The study staff doing chart review and data entry will be blinded to the patient and provider assignments to avoid unintended bias. The statistician analyzing the data will also be blinded to the study assignments.

For studies involving treatment or diagnosis, provide information about standard of care at Partners (e.g., BWH, MGH) and indicate how the study procedures differ from standard care. Provide information on available alternative treatments, procedures, or methods of diagnosis.

This study involves reviewing patient educational materials, completing surveys and conducting medical chart review. No diagnostic tests or treatments will be offered or administered as part of this study.

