threshold *and* receive treatment that matches their preference. A logistic regression model with the generalized estimating equations (GEE) approach will be used to compare the rates of decision quality of the DA-A and DA-B groups and account for the clustering of patients within providers.[4] Analysis will start by testing the interaction between the two intervention factors. It is plausible that an interaction between DAs and type of surgeon report exists for this analysis. Thus, the effective sample size will be limited to 117 per group when the comparisons are stratified by the type of surgeon report. The study has 89% power to detect a difference in the percentage of patients with high decision quality of 18%, from 65% in DA-B group to 83% in DA-A group.

For hypothesis 1.2, an interaction between DAs and PPR report is unlikely so there is no need to account for clustering within the same provider, thus, we will use a two-sample t-test to compare the mean knowledge score between the two groups. With approximately 560 patients from each group, we can invoke the Central Limit Theorem and use a two-sample t-test to compare mean knowledge score between the two groups, even if the knowledge score is not normally distributed. The study will have 80% power to detect a difference as small as 3.3% in total knowledge scores assuming the SD is 20%. For hypothesis 1.3, patient's treatment preference will be assessed before the surgeon visit so again, there is no need to account for clustering. A X² test will be used to compare the percentage of patients with clear treatment preference between the two groups. Hypothesis 2.1 will use a linear regression model with the GEE approach and hypothesis 2.2 will use logistic regression with GEE approach to account for clustering of patients within surgeons for these analyses.

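### The surgeon-clustered GEE analyses need a pre-specified working correlation and small-sample correction; with uncorrected robust errors and few surgeons, type I error may exceed 5%

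*SAP*

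**What the plan says.** The SAP's paragraph on hypothesis 1.1 gives the primary analysis: "A logistic regression model with the generalized estimating equations (GEE) approach will be used to compare the rates of decision quality", in order to "account for the clustering of patients within providers". It adds: "Analysis will start by testing the interaction between the two intervention factors". Because an interaction is considered plausible, power is given for comparisons stratified by type of surgeon report: 89% for 65% versus 83%, with an effective 117 patients per group. Hypotheses 2.1 and 2.2 also use GEE, as do the heterogeneity tests wherever patients cluster within providers.

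The two factors are randomised at different levels (Protocol, Randomization and blinding). For the decision aid, "A computer-generated randomization allocation sequence will be created for patients from each site", so this factor varies within surgeon. For the report, "Within each site, surgeons will be divided into two groups with similar patient volume", and then "One of the two groups will be randomly assigned to usual care and the other to receive the in-visit worksheet". This factor is constant within surgeon. On sites, Research Design and Methods says: "The study will enroll patients at three sites".

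The opening part of the SAP was not available to this review. The text that was available does not give the variance estimator, working correlation, reference distribution, small-sample correction, number of surgeons, intracluster correlation (ICC) or alpha.

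**The concern.** GEE is most often reported with sandwich (robust) standard errors and a z-test. That combination relies on a large number of clusters. With few clusters the sandwich is too small on average and too variable, and z ignores that variability. The clusters here are surgeons at three hospitals, and a comparison within one report arm uses only about half of them.

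The primary comparison, the interaction test that decides how it is presented, and any test of the surgeon report for Aim 1 could therefore have p-values that are too small and intervals that are too narrow. Leaving the estimator open also matters in itself, because two analyses that both fit the SAP's description can have very different error rates.

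**Working it through.** **Plan's own figure.** Two-sided alpha of 0.05 is assumed.
- Mean rate = (0.65 + 0.83)/2 = 0.74
- SE under the null = √(2 × 0.74 × 0.26/117) = 0.05735
- SE under the alternative = √((0.65 × 0.35 + 0.83 × 0.17)/117) = 0.05613
- z = (0.18 − 1.960 × 0.05735)/0.05613 = 1.204, so power = 88.6%

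The stated 89% is reproduced, with a normal reference.

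**How many surgeons?** If 117 is the effective size of 840/4 = 210 patients (840 being the protocol's expected one-week completers), the design effect is 210/117 = 1.79. Mean cluster size is then 1 + 0.79/ICC, and the number of surgeons is 840 divided by that: about 10 at ICC 0.01, 21 at 0.02, 31 at 0.03 and 50 at 0.05. Starting from 716 or 1,120 patients gives a design effect of 1.53 or 2.39 instead. The figures do not fix the count, so 8 to 40 is used as an assumed range.

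**Simulated type I error.** Assumptions: 840 patients, null rate 74%, beta-binomial surgeon effects with ICC 0.01 or 0.05, coefficient of variation of surgeon volume 0.5, decision aid 1:1 within surgeon, surgeons paired on volume for the report, and no site effects or site term. The model is an exchangeable logistic GEE. There were 3,000 replicates (1,500 for model-based errors). Monte Carlo error is about 0.4–0.7 points, and up to about 1 point for the 1,500-replicate runs. Ranges run over the two ICCs; column heads are total surgeons.

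Uncorrected robust SE with z:

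| Test | 8 | 12 | 20 | 40 |
|---|---|---|---|---|
| Decision aid | 10.5–12.8% | 9.4–9.5% | 8.1–8.7% | 6.0–6.8% |
| Decision aid within one report arm | 20.3–20.7% | 14.3–16.4% | 9.8–10.3% | 8.2–8.7% |
| Interaction | 15.8–16.9% | 11.5–12.4% | 8.0–9.0% | 6.9–7.1% |
| Surgeon report | 16.6–18.7% | 10.6–13.8% | 8.6–10.2% | 6.4–7.8% |

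Other settings agree closely. Independence working correlation, a 70% null rate and an ICC matched to the 1.79 design effect gave 10.7%, 9.9%, 8.1% and 5.6% for the decision aid, and 18.4%, 14.9%, 10.3% and 6.7% within one arm. A further repeat gave 7–8% for the decision aid and about 11% within one arm at 20 surgeons.

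Model-based SE with z, exchangeable correlation correctly specified:
- Decision aid 4.5–5.7%, within one arm 3.8–5.6%, interaction 4.3–5.7%
- Surgeon report 17.3–18.0% with 8 surgeons, 12.5% with 12, 9.1% with 20, 6.7–7.1% with 40

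Mancl-DeRouen SE with t (degrees of freedom = clusters minus parameters), over 8 to 40 surgeons:
- Decision aid 2.9–5.3%, within one arm 1.5–5.0%, interaction 1.8–4.6%, surgeon report 3.3–4.8%

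**Power with a t reference.** Take the plan's effective 117 per group as given. The noncentrality is 1.960 + 1.204 = 3.164, and degrees of freedom are surgeons in the stratum minus 2.

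| Surgeons per stratum | df | Critical t | Power |
|---|---|---|---|
| 10 | 8 | 2.306 | about 79% |
| 6 | 4 | 2.776 | about 66% |
| 4 | 2 | 4.303 | about 42% |

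These figures are before any variance inflation from the correction.

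**The case against.** The strongest reply is that the available text never says robust errors will be used. With model-based errors and a correct exchangeable correlation, every decision aid test stays near 5%, because the aid is randomised by patient within surgeon. That stands. A reader might infer that the primary test's false-positive rate is in fact above 5%; the documents do not support this, since it depends on an estimator and a surgeon count that are not in the available text. With 40 surgeons the robust excess for the decision aid is only about 1–2 points.

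Second, the surgeon count, the ICC and perhaps the small-sample method may be in the part of the SAP that was not available. That also stands: the plan as a whole cannot be said to lack them.

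Third, the available SAP text describes no separate test of the report's main effect. Hypotheses 1.1 to 1.3 all compare decision aids. The report figures therefore apply only to a test made for Aim 1, which does name that intervention.

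Fourth, a reader might infer from the single draw per site that few surgeon allocations are possible and that this limits any p-value for the report. No randomisation test is planned, and the protocol does not say whether chance played a part in forming the volume groups, so this does not follow. How surgeons are allocated is a separate design choice.

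Fifth, the correction costs power. It does when surgeons are few, but the uncorrected alternative reaches that power by rejecting too often under the null.

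**Conclusion.** The concern holds conditionally. If the surgeon-clustered analyses use uncorrected robust errors with a z-test, nominal 5% tests may run at about 9–13% for the decision aid with 8–12 surgeons, 7–9% with 20 and 6–7% with 40. Within one report arm the figures are about 14–21%, 10–11% and 8–9%. The interaction, which is tested first, runs at about 7–17% across the range. Choosing model-based errors removes the problem for the decision aid only if the working correlation is right. It leaves any surgeon-report test inflated when surgeons are few.

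These sizes rest on assumptions that are not in the available text: 8 to 40 surgeons, ICC 0.01 to 0.05, moderately unequal surgeon volumes and two-sided alpha of 0.05. The direction did not change across the settings tried; the size depends mainly on the surgeon count.

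**What to change.** For every surgeon-clustered GEE analysis (hypothesis 1.1, the interaction, comparisons within report arms, hypotheses 2.1 and 2.2, and the clustered heterogeneity tests), the SAP should state:

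- the number of surgeons, in total and per report arm;
- the working correlation;
- a small-sample variance correction, Mancl-DeRouen or Kauermann-Carroll;
- a t reference, with a written rule deriving its degrees of freedom from the number of surgeons;
- site as a covariate, since both randomisations were done by site.

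The cost is SAP wording and a software option, plus wider intervals. The test is conservative with about 8 surgeons (as low as 1.5% within one arm). Power for the stratified comparison falls below the stated 89% when surgeons are few, to roughly 79% with 10 per stratum and 66% with 6 before variance inflation. It should be restated once the count is given.

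Three sites add two parameters. Under a clusters-minus-parameters rule, a stratum of 10 surgeons then has 10 − 4 = 6 degrees of freedom rather than 8, and a stratum of 4 has none. The rule should say in advance what is done in a stratum that small. The simulations above did not include site terms.

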Knee and Hip Osteoarthritis	
 • Diagnosis of knee or hip OA • Adults, age 21 or older • Scheduled new patient visit with participating orthopaedic specialist 	
 • Prior partial or total knee or hip replacement surgery on joint of concern within 5 years • Hip fracture or aseptic necrosis at any time in 12 months prior to visit • Rheumatoid arthritis or psoriatic arthritis • Does not read or write in English or Spanish • Unable to consent for self due to cognitive or other medical issue(s) • Prior decision aid order for joint of concern

Patient participants will be surveyed at three time points, before their visit with the surgeon, about one week after the visit, and again 12 months after the visit. Data from our previous studies suggests that we will have about 65 eligible new patients each month for the study enrollment period. We plan to enroll patients for about 12 months and estimate 1,120 patients will complete the first assessment in-clinic or before the visit with the surgeon, 840 (75%) will complete the second assessment one week after the visit, and 716 will complete the third assessment about one year after the visit. The sample size calculations consider both the potential for interaction effects between the interventions as well as the potential impact of clustering of patient participants within surgeons. Figure 2 offers a more detailed look at the projected screening and enrollment numbers.

Figure 2: CONSORT Flow diagram with estimates for screening, enrollment and response rates

Legend: PDA=patient decision aid, T1=in clinic before surgeon visit, PRO=patient reported outcomes; T2=1 week post visit; T3=6-12 month post visit

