20. Study data will be cleaned, surveys will be scored, analyzed and manuscripts will be prepared for publication.

Clinician surveys:

Participating clinicians will complete a short survey for a subset of their participating patients. The survey will include questions about satisfaction with the visit and rating of the quality of the decision. Research coordinators will approach the clinician in person with paper survey shortly after the initial visit. If they are not able to connect in person, they will send an email with the survey for each patient and will make up to three reminders via email to encourage the surgeon complete the survey.

All study staff are CITI certified and will receive training from the PI and program manager in the study protocol.

Outcomes:

This study will capture three main types of outcomes – these include patient-reported measures related to decision making (e.g. decision quality, decision making process and regret), patient-reported health outcomes (e.g. knee and hip pain, quality of life and functioning) and medical treatments received by participants.

We will collect the measures listed below. Table 3 shows the measures assessed at each time point as part of this study and the estimated burden on participants.

Measures:

Decision Making Measures (timing of use)

1. Hip OA and Knee OA Decision Quality Instruments (T1, T2, T3): Each DQI contains 5 decision-specific, multiple-choice knowledge items, 5 decision-specific goals and concerns (rated on an 11 point importance scale), one treatment preference item. The DQI results in a knowledge score (0-100%) and a concordance score (0-100%) indicating the percentage of patients who received treatments that matched their stated preference, and an involvement score (0-100%) with higher scores indicating more patient involvement in decision making. The minimal important changes (MIC) in knowledge and concordance scores are 10% (14).

2. Decision Process Score (T2, T3): 7 items that assess the decision-making process including whether options, outcomes and preferences were discussed. A total score is generated and scaled to (0-100%) with higher scores indicating more patient involvement in decision making. 3 items that assess general satisfaction with the visit.(9)

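### The tests for hypotheses 1.2 and 1.3 use neither site nor joint, a small loss of precision that costs nothing to recover; the reason given in 1.2 for ignoring clustering should be replaced in the same edit

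*SAP*

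**What the plan says.** **Allocation.** The protocol (Randomization and blinding) says of patients: "A computer-generated randomization allocation sequence will be created for patients from each site". For surgeons it says: "Provider randomization will be stratified by site". It describes no blocks for the patient sequences and does not name joint as a stratification factor.

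**Outcome.** The protocol's list of measures gives the instruments as "Hip OA and Knee OA Decision Quality Instruments (T1, T2, T3): Each DQI contains 5 decision-specific, multiple-choice knowledge items". The treatment preference item belongs to the same joint-specific instruments.

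**Hypothesis 1.2.** The SAP compares mean knowledge scores with a two-sample t-test. It sets clustering aside because "an interaction between DAs and PPR report is unlikely so there is no need to account for clustering within the same provider". The sample size statement begins "With approximately 560 patients from each group" and claims 80% power for 3.3 points at an SD of 20. The available text names no time point for this test.

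**Hypothesis 1.3.** The reason here is a different one: "patient's treatment preference will be assessed before the surgeon visit so again, there is no need to account for clustering". The test is then given: "A X² test will be used to compare the percentage of patients with clear treatment preference between the two groups".

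**Expected numbers.** The protocol (Research Design and Methods) says the investigators "estimate 1,120 patients will complete the first assessment in-clinic or before the visit with the surgeon, 840 (75%) will complete the second assessment".

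In the available SAP text joint appears only as a possible effect modifier, in the paragraph on heterogeneity. The SAP text that comes before the missing-data paragraph was not available, so every statement here about what the SAP omits covers the remaining text only.

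**The concern.** Two features of the design point to covariates that the tests do not use. Site defines the allocation sequences, and joint decides which knowledge questions a patient answers. If mean scores differ by site or joint, that variation stays in the error term of an unadjusted test. Both variables will be in the database, so the precision is given up for nothing.

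The clustering sentence for 1.2 is a separate matter. Report type is assigned to surgeons. Ruling out a DA-by-report interaction removes one possible source of between-surgeon variation in the DA effect. It does not make patients of the same surgeon independent, and it leaves other sources of variation in place. A reader who checks the argument will find that it does not reach its conclusion, although a correct argument is available.

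At stake are a slightly wider confidence interval on two secondary hypotheses and a justification that would not survive peer review as worded.

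**Working it through.** **Inputs.** From the SAP: 560 per group, SD 20, difference 3.3, power 80%. From the protocol: 1,120 patients at T1 (560 per group) and 840 at T2 (420 per group). Assumed, because the available text does not give them: two-sided 5% significance, hip-knee gap and mix, site differences, the proportion with a clear preference, number of surgeons and surgeon variance.

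**1. Reproduce the plan's figure.** Power = Φ(3.3 / (20·√(2/560)) − 1.960) = Φ(2.761 − 1.960) = 78.8%. The detectable difference at 80% power is 2.8016 × 20 × √(2/560) = 3.35. This fits the stated 80% and 3.3 after rounding. A one-sided 5% test would give 86.8% and does not fit.

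**2. Hypothesis 1.2, adjusting for joint.** With a share m of one joint and a gap d between joints, the residual variance is 400 − m(1−m)d², so

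detectable difference = 2.8016 × √(400 − m(1−m)d²) × √(2/n).

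| Gap d (m = 0.5) | 0 | 5 | 10 | 15 |
|---|---|---|---|---|
| n = 560 per group | 3.35 | 3.32 | 3.24 | 3.10 |
| n = 420 per group | 3.87 | 3.84 | 3.74 | 3.58 |

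At d = 10 the variance is 400 − 25 = 375 (SD 19.36). Power for 3.3 points at 560 per group becomes Φ(3.3/(19.36·√(2/560)) − 1.960) = Φ(0.89) = 81%. With a 25:75 mix, the 560-per-group row reads 3.35, 3.33, 3.27, 3.17.

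**3. Hypothesis 1.2, adjusting for site alone.** With three equal sites at −d, 0 and +d, the residual variance is 400 − 2d²/3. For d = 2.5, 5 and 10 the detectable difference at 560 per group is 3.33, 3.28 and 3.06.

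**4. Hypothesis 1.3, stratifying by site.** With overall proportion p and three equal sites at p − g, p and p + g,

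detectable difference = 2.8016 × √(2(p(1−p) − 2g²/3)/560).

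| Site spread g (points) | 0 | ±5 | ±10 | ±15 |
|---|---|---|---|---|
| p = 0.6 | 8.20 | 8.17 | 8.09 | 7.94 |
| p = 0.7 | 7.67 | 7.64 | 7.55 | 7.39 |
| p = 0.8 | 6.70 | 6.66 | 6.56 | 6.38 |

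**5. Does ignoring surgeons distort the 1.2 test?** This was simulated with 4,000 replicates per cell, so the simulation error at 5% is √(0.05 × 0.95/4000) = 0.3 points. Assumed: 1,120 patients, 12 surgeons, three sites, a 10-point hip-knee gap, surgeon and site each 5% of variance, and simple allocation. The table gives type I error (%) by the SD of the DA effect across surgeons.

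| SD of DA effect (points) | 0 | 1 | 2 | 3 |
|---|---|---|---|---|
| t-test | 5.2 | 5.6 | 7.7 | 10.8 |
| site + joint model, ordinary SE | 5.1 | 5.9 | 8.4 | 11.4 |
| surgeon-clustered SE, small-sample correction | 5.4 | 5.2 | 5.3 | 5.5 |

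The first column is the relevant one. Surgeon differences in mean score do not inflate the error when DAs are randomised within surgeon. Only variation of the DA effect itself does, and adjusting for site and joint does not remove that.

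**6. Time point.** At T2, power for 3.3 points is Φ(3.3/(20·√(2/420)) − 1.960) = Φ(0.43) = 66.7%, and the detectable difference is 3.87. Since 560 is half of 1,120, the SAP's figure belongs to T1.

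**The case against.** An unadjusted t-test or chi-squared test is a legitimate analysis of a patient-randomised comparison. Joint is not a stratification factor, and no blocks are described for patients, so the design does not compel either covariate. Every gain shown above comes from an assumed gap. The heterogeneity analysis already models DA interactions with joint and with surgeon characteristics. The SAP's reference list also contains notes on cluster randomised trials that the available text never cites, and the protocol says clustering was considered in the sample size, so the unavailable SAP text may well treat clustering. All of this stands, and it keeps the point minor. It does not remove it: interaction tests do not sharpen the main comparison, and the adjustment needs no new data.

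Three stronger readings are tempting, and the documents do not support them.

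- *That ignoring surgeons makes the tests invalid.* Patients are individually allocated within site, so DAs cross surgeons. The 10.8% above needs 12 surgeons (assumed), a DA effect whose SD across surgeons is nearly the whole 3.3-point target, and inference to surgeons beyond those in the trial, which the available SAP text does not claim. If knowledge is taken at T1, before the visit, there is little reason to expect such variation.
- *That the power for 1.2 is overstated because no time point is given.* The 560 per group points to T1, and the unavailable text may say so outright.
- *That only 1.2 lacks joint.* The chi-squared test for 1.3 has no joint term either.

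**Conclusion.** A minor point, and an improvement at no cost. In the available text both tests omit site and joint. They remain unbiased and keep their type I error under a DA effect common across surgeons. The loss is about 0.1 points of detectable difference on each hypothesis under the assumed 10-point hip-knee gap (1.2) or ±10-point site spread (1.3). It is about zero if sites and joints do not differ. Two-sided 5% significance, the gaps, the mix and the 70% clear-preference rate are all assumptions.

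The reason given for ignoring clustering in 1.2 does not follow from an absent DA-by-report interaction. The decision itself can stand on individual randomisation plus a common DA effect. The time point needs confirming, not correcting. It matters more than the adjustment, because moving to T2 would raise the detectable difference from 3.35 to 3.87.

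**What to change.** Suggested SAP wording for 1.2:

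> Mean knowledge score at T1 [confirm] will be compared with a linear model with terms for DA, site and joint. DAs are randomised to individual patients within site and so cross surgeons; assuming a DA effect common across surgeons, no design effect for clustering is applied.

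If T1 is confirmed, the pre-visit argument already used for 1.3 can be cited here too. If T2 is meant, restate the power for 420 per group.

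For 1.3:

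> The percentage with a clear preference will be compared with a Mantel-Haenszel test stratified by site and reported as a risk difference.

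Joint may be added as a further stratum.

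A surgeon-clustered analysis of 1.2, with a small-sample correction and t reference on the number of surgeons minus 1 degrees of freedom, is an optional sensitivity check. It should not be primary. In the simulated 12-surgeon case with a common effect of 3.3 points, its power was 77.8%, against 84.8% for the site and joint model and 80.0% for the t-test.

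The cost is a few lines of text. Joint and physician are kept even for non-responders (protocol, Study Procedures, item 19), and site is known from the allocation sequence.
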